11.2 Record Retention

To enable evaluations and/or audits from regulatory authorities or Iterum, the Investigator agrees to keep records, including the identity of all participating patients (sufficient information to link records, e.g., CRFs and hospital records), all original signed informed consent forms, copies of all CRFs, SAE forms, source documents, and detailed records of treatment disposition, and adequate documentation of relevant correspondence (e.g., letters, meeting minutes, telephone call reports). The records should be retained by the Investigator according to ICH, local regulations, or as specified in the Clinical Study Agreement, whichever is longer.

If the Investigator becomes unable for any reason to continue to retain study records for the required period (e.g., retirement, relocation), Iterum should be prospectively notified. The study records must be transferred to a designee acceptable to Iterum, such as another Investigator, another institution, or to Iterum. The Investigator must obtain Iterum's written permission before disposing of any records, even if retention requirements have been met.

12 ETHICS

12.1 Institutional Review Board (IRB)/Independent Ethics Committee (IEC)

It is the responsibility of the Investigator to have prospective approval of the study protocol, protocol amendments, informed consent forms, and other relevant documents, e.g., recruitment advertisements, if applicable, from the IRB/IEC. All correspondence with the IRB/IEC should be retained in the Investigator File. Copies of IRB/IEC approvals should be forwarded to Iterum or its agent

The only circumstance in which an amendment may be initiated prior to IRB/IEC approval is where the change is necessary to eliminate apparent immediate hazards to the patients. In that event, the Investigator must notify the IRB/IEC and Iterum in writing immediately after the implementation.

12.2 Ethical Conduct of the Study

The study will be conducted in accordance with the Declaration of Helsinki on Ethical Principles for Medical Research Involving Human Patients, adopted by the General Assembly of the World Medical Association (2013).

In addition, the study will be conducted in accordance with the protocol, the International Conference on Harmonisation (ICH) guideline on Good Clinical Practice (GCP), and applicable local regulatory requirements and laws.

12.3 Patient Information and Consent

All parties will ensure protection of patient personal data and will not include patient names on any sponsor forms, reports, publications, or in any other disclosures, except where required by laws. In case of data transfer, Iterum will maintain high standards of confidentiality and protection of patient personal data.

Iterum Therapeutics US Limited. Amendment 02: 27March 2018

Clinical Trial Protocol: IT-004-401

The informed consent form must be in compliance with ICH GCP, local regulatory requirements, and legal requirements.

The informed consent form used in this study, and any changes made during the course of the study, must be prospectively approved by both the IRB/IEC and Iterum before use.

The Investigator must ensure that each study patient, or his/her legally acceptable representative, is fully informed about the nature and objectives of the study and possible risks associated with participation. The Investigator, or a person designated by the Investigator, will obtain written informed consent from each patient or the patient's legally acceptable representative before any study-specific activity is performed. The Investigator will retain the original of each patient's signed consent form.

Reporting of Safety Issues and Serious Breaches of the Protocol or ICH GCP

In the event of any prohibition or restriction imposed (i.e., clinical hold) by an applicable Competent Authority in any area of the World, or if the Investigator is aware of any new information which might influence the evaluation of the benefits and risks of the investigational product, Iterum should be informed immediately.

In addition, the Investigator will inform Iterum immediately of any urgent safety measures taken by the Investigator to protect the study patients against any immediate hazard, and of any serious breaches of this protocol or of ICH GCP that the Investigator becomes aware of.

13 DEFINITION OF END OF STUDY

13.1 End of Study in Participating Countries

End of Study in all participating countries is defined as the TOC Visit.

14 SPONSOR STUDY TERMINATION CRITERIA

Premature termination of this study may occur because of a regulatory authority decision, change in opinion of the IRB/IEC, drug safety problems, or at the discretion of Iterum.

If a study is prematurely terminated, Iterum will promptly notify the Investigator and the Investigator must also inform the IRB/IEC. After notification, the Investigator must contact all participating patients and the hospital pharmacy (if applicable) within 90 days. Investigator must also inform the IRB/IEC. As directed by Iterum, all study materials must be collected and all CRFs completed to the greatest extent possible.

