- 9. Patient's urine culture results, if available at study entry, identify more than 2 microorganisms regardless of colony count or a potential fungal pathogen
- 10. Patient's urine culture results, if available at study entry, identifies causative uropathogen for the presenting illness to be resistant to ciprofloxacin
- 11. Patient has severe chronic kidney disease, or is receiving hemodialysis, or peritoneal dialysis or had a renal transplant
- 12. Patient is known to have severe neutropenia
- 13. Patient is known to be pregnant
- 14. Patients with uncontrolled diabetes mellitus
- 15. Patients with a known history of myasthenia gravis
- 16. Patients who require concomitant administration of tizanidine
- 17. Patients with a history of allergy to quinolones
- 18. Patient is considered unlikely to survive the study period or has a rapidly progressive or terminal illness, including septic shock, associated with a high risk of mortality

Test Product, Dose, and Mode of Administration:

Patients will receive ciprofloxacin 250 mg, to be taken by mouth twice daily for 3 days.

Formulation and Packaging:

The site Investigator or designee will provide the patient with either a pharmacy prescription or a supply for a 3 day (250 mg BID) course of generic ciprofloxacin for the treatment of their uUTI. The generic ciprofloxacin will be supplied by a local pharmacy, in the form of a filled prescription, that includes 6- 250 mg tablets of ciprofloxacin.

Preparation and Dispensing:

All generic ciprofloxacin will be prepared and provided to the patient via a prescribing pharmacy prescription, or, provided by the Investigator or designee.

Administration:

The patient will receive one 3-day treatment course of generic ciprofloxacin, with instructions to take one tablet or capsule of oral ciprofloxacin 250 mg twice daily beginning day 1 through 3 (+ 1 day).

In the event a patient's first dose is taken in the PM on Day 1, the patient will be expected to take an AM dose on Day 4 to receive the 6 doses of ciprofloxacin, and the EOT visit will occur on day 4 instead of day 3.

Safety Assessments

Safety will be assessed by means of collection of adverse events. Adverse events will be collected at every visit, beginning from the signing of Informed Consent.

Efficacy Assessments:

The assessment of clinical response includes a review of the following symptoms: urinary frequency, urinary urgency, pain or burning on micturition, suprapubic pain and gross hematuria.

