3 STUDY DESIGN

This prospective, Phase 4, open label, multi-center study documents the clinical and microbiologic response of adult women patients with uUTI treated empirically with ciprofloxacin. Since UTIs in males are classified as complicated, males will not be included in this study. Approximately 250 adult women with uUTI will receive oral ciprofloxacin 250 mg twice daily for 3 days.

The primary outcome measure for efficacy evaluation will be the overall response on Day 12 (+/- 1 day). For the primary efficacy evaluation, these percentages will be based on a microbiologic-modified intent to treat population (m-MITT). The m-MITT population will be comprised of all patients who received at least one dose of ciprofloxacin and had $\geq 10^5$ CFU/mL of a baseline pathogen isolated from a urine culture specimen taken at baseline, prior to initiation of ciprofloxacin therapy.

See Appendix 1, Schedule of Activities Table.

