5.2.2 Preparation and Dispensing

The patient will receive one 3-day treatment course of generic ciprofloxacin, with instructions to take one tablet or capsule of oral ciprofloxacin 250 mg twice daily beginning day 1 through 3 (+ 1 day).

In the event a patient's first dose is taken in the PM on Day 1, the patient will be expected to take an AM dose on Day 4 to receive the 6 doses of ciprofloxacin, and the EOT visit will occur on day 4 instead of day 3.

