6.3.2 Post Test of Cure (TOC) Day 21 (+/- 3 days)

Call patient to assess for resolution of uUTI symptoms

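### Protocol Section 14 gives one 90-day limit for contacting patients after any early stop, including a safety stop, and so does not ensure contact during the 3-day course or the adverse event collection period

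*Protocol*

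**What the plan says.** Protocol Section 14 gives the grounds for an early stop: "Premature termination of this study may occur because of a regulatory authority decision, change in opinion of the IRB/IEC, drug safety problems", or the sponsor's discretion. The first step after a stop is "If a study is prematurely terminated, Iterum will promptly notify the Investigator and the Investigator must also inform the IRB/IEC". The next is "After notification, the Investigator must contact all participating patients and the hospital pharmacy (if applicable) within 90 days". That limit is not divided by reason for stopping.

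The schedule it has to serve is set elsewhere in the protocol:

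- **Treatment.** Section 5.2.2: "The patient will receive one 3-day treatment course of generic ciprofloxacin". Sections 3.1 and 5.2.2 add that a patient who starts in the evening of Day 1 takes her sixth and last dose on the morning of Day 4.
- **Adverse events.** Sections 8.2 and 8.11 collect them from consent to the test-of-cure (TOC) visit, which Section 6.3.1 places on Day 12, plus or minus 1 day. Section 13.1 defines the end of study as that visit.
- **Last scheduled contact.** Section 6.3.2 adds a telephone call on Day 21, plus or minus 3 days, to ask whether symptoms have resolved. The Schedule of Activities has no adverse event entry at that point.

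On supply, the Synopsis says "The generic ciprofloxacin will be supplied by a local pharmacy, in the form of a filled prescription". The Synopsis and Sections 3.1 and 5.2.1 also allow the site to hand over the drug. Section 14 mentions only a hospital pharmacy, where applicable.

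The SAP text available does not address contact with patients after termination.

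**The concern.** A contact limit after a safety stop is there to reach patients while contact can still make a difference: before the remaining doses are taken, or while adverse events are still being collected. Here the course is 3 days and collection lasts less than two weeks, but the limit is 90 days. The urgency in Section 14 attaches to the step from sponsor to site; the step from site to patient has only the 90-day limit.

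Participant protection is at stake, together with the completeness of safety data at the moment it would matter most. The endpoint, sample size, analysis populations and planned summaries are unaffected. The pharmacy wording is a smaller mismatch in the same clause, because it names a route that the protocol does not otherwise describe for this drug.

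**Working it through.** The 90 days is a chosen limit with no derivation in the protocol, so there is no calculation to reproduce. The check is day arithmetic against the protocol's own schedule.

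**Inputs**

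- Contact limit: 90 days from notification of the investigator (Section 14).
- Latest planned dose: Day 4, morning (Sections 3.1 and 5.2.2).
- Latest TOC visit, which ends adverse event collection and the study: 12 + 1 = Day 13 (Sections 6.3.1, 8.2 and 13.1).
- Latest scheduled call: 21 + 3 = Day 24 (Section 6.3.2).

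**Deadline for one patient.** If she is on study day *d* when the site is notified, the limit expires on day *d* + 90.

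**Patient on Day 1 at notification.** Deadline = 1 + 90 = Day 91. The deadline falls:

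- after a Day 4 last dose by 91 − 4 = 87 days (after a Day 3 last dose, 91 − 3 = 88 days);
- after the latest TOC visit by 91 − 13 = 78 days;
- after the latest scheduled call by 91 − 24 = 67 days.

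**All other patients.** A later *d* only moves the deadline later:

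- on drug (*d* = 1 to 4): Day 91 to Day 94;
- in the adverse event collection period (*d* = 1 to 13): Day 91 to Day 103;
- within the schedule at all (*d* = 1 to 24): Day 91 to Day 114.

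The smallest of these, Day 91, is beyond Day 24. So the limit expires after the end of scheduled participation for every patient who is in the study when the site is told.

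**Time left, seen from Day 1.** There are 4 − 1 = 3 days to the latest planned dose, 13 − 1 = 12 days to the latest TOC visit and 24 − 1 = 23 days to the latest call, against a limit of 90.

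**Sensitivity.** The Schedule of Activities lets the call confirming receipt of medication be made a day late. If one assumes that dosing also began a day late, the last dose could fall on Day 5, and the first gap becomes 91 − 5 = 86 days. The conclusion does not change.

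**Does another clause set a time for telling patients?** None of those that bear on safety does:

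- Section 6.4 allows withdrawal of a patient for safety at any time.
- Section 12.1 allows an amendment ahead of ethics approval to remove an immediate hazard.
- Section 12.2 binds the study to good clinical practice.
- Section 12.3 requires the investigator to inform the sponsor at once of urgent safety measures and new benefit-risk information.

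**The case against.** The strongest reply is that 90 days is a ceiling. Nothing in Section 14 directs or invites a site to wait, and a careful site would telephone at once after a safety stop. The provisions in Sections 6.4 and 12.1 to 12.3 also apply, so Section 14 is not the only safeguard. This stands, and it limits the claim. A reader might infer that the rule leaves women on drug unprotected. The text does not support that; it supports only that timely contact is not guaranteed.

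A reader might also infer that late contact removes any chance to learn of adverse events. That goes too far. Section 8.1 follows known events until they resolve or stabilize, and Section 8.2 keeps suspected related serious events reportable after the TOC visit. Both depend on the site knowing of the event, so they narrow the gap without closing it. Nor does the Day 21 call extend adverse event collection: the relevant window ends by Day 13, not Day 24.

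On the pharmacy, a reader might infer that a woman holding an unfilled prescription falls outside the clause. She does not: the clause covers all participating patients, and Section 5.2.3 already has the site telephone the patient or pharmacy on Day 1. What remains is a mismatch of wording.

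Finally, the clause acts only if the study stops early, and a long ceiling beside a short course is a poor fit rather than a flat contradiction. Both remarks are fair. They bear on the weight of the point, not on whether it is true.

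**Conclusion.** The point holds in limited form. Section 14 applies one 90-day limit to every kind of early termination, and that limit does not fit a study whose last planned dose is on Day 3 or 4, whose adverse event collection ends by Day 13 and whose last scheduled call is by Day 24. For a woman on Day 1 at notification, a site could comply as late as Day 91, which is 87, 78 and 67 days past the latest of those dates.

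These gaps describe what the rule permits. They do not estimate how late sites would be, and they do not measure risk. They assume that the 90 days run from the day the investigator is notified, and that visits and doses keep to the protocol windows. Follow-up of adverse events already known, or of a pregnancy, can run beyond Day 24 for individual patients. The result is a participant-protection point that is worth amending, with no consequence for the statistical analysis.

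**What to change.** The sponsor should reconcile the contact limit in Section 14 with the course in Section 5.2.2, the visits and call in Section 6.3 and the adverse event period in Section 8.2, treating safety stops separately from administrative ones. The sponsor's safety function should set the figure; none is proposed here. The same edit should bring the reference to a hospital pharmacy into line with the supply routes that the protocol describes: a prescription filled at a local pharmacy, or supply by the site.

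The cost is about one sentence in a protocol amendment. Sites already telephone patients and pharmacies under Sections 5.2.3 and 6.3.2, so they would make the same calls sooner. The SAP needs no change.

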15 PUBLICATION OF STUDY RESULTS

Publication of study results is discussed in the Clinical Study Agreement.

15.1 Communication of Results by Iterum

Iterum fulfills its commitment to publicly disclose the results of studies through registration and posting of the results of this study on clinicaltrials.gov.

If posting of study results to clinicaltrials gov jeopardizes a planned publication of the study results, a Pending Full Publication notice is substituted for the synopsis until the study results publication has been issued or 2 years have elapsed, whichever occurs first.

15.2 Publications by Investigators

Iterum has no objection to publication by the Investigator of any information collected or generated by the Investigator, however, to ensure against inadvertent disclosure of Confidential Information or unprotected Inventions, the Investigator will provide Iterum an opportunity to review any proposed publication or other type of disclosure before it is submitted or otherwise disclosed.

The Investigator will provide manuscripts, abstracts, or the full text of any other intended disclosure (poster presentation, invited speaker or guest lecturer presentation, etc.) to Iterum at least 30 days before they are submitted for publication or otherwise disclosed. If any patent action is required to protect intellectual property rights, the Investigator agrees to delay the disclosure for a period not to exceed an additional 60 days.

The Investigator will, on request, remove any previously undisclosed Confidential Information (other than the study results themselves) before disclosure.

If the study is part of a multi-center study, the Investigator agrees that the first publication is to be a joint publication covering all centers. However, if a joint manuscript has not been submitted for publication within 12 months of completion or termination of the study at all participating sites, the Investigator is free to publish separately, subject to the other requirements of this section.

For all publications relating to the study, the Institution will comply with recognized ethical standards concerning publications and authorship, including Section II - "Ethical Considerations in the Conduct and Reporting of Research" of the Uniform Requirements for Manuscripts Submitted to Biomedical Journals, http://www.icmje.org/index.html#authorship, established by the International Committee of Medical Journal Editors.

Publication of study results is also provided for in the Clinical Study Agreement between Iterum and the Institution. In this section entitled Publications by Investigators, the defined terms shall have the meanings given to them in the Clinical Study Agreement.

Appendix 1 Schedule of Activities

	SCREENING PERIOD	TREATM	ENT PERIOD	FOLLOW-	UP PERIOD
Protocol Activity	Screening (D1)	Baseline (D1)	EOT ¹ (D3 or D4) (+ 1 day)	TOC (D12) (+/- 1 day)	Post TOC (D21) (+/- 3 days)
Informed Consent	X				
Medical History and Demographics	X				
Temperature	X				
Height and Weight	X				
Urine dipstick	X				
Urinalysis		X			
Urine Culture and Sensitivity		X	X	X	
Previous Drug and Non-Drug Treatments	X				
Concomitant Medications	X		X	X	
Treatment ¹		X (for	3 days)		
Treatment Compliance Check ²		X^2	X		
Patient Dosing Diary		Distribute	Collect		
Adverse Events	X		X	X	

Patient Symptom Assessment Questionnaire	X	X	X	
Investigator-Determined Clinical Response Evaluation		X	X	
Post TOC Telephone Contact				X

¹In the event that the first dose of ciprofloxacin is taken in the morning on Day 1, the EOT visit will be on day 3 (+1 day). In the event that the first dose of ciprofloxacin is taken in the evening on Day 1, the EOT visit will be on day 4 (+1 day).

²Site personnel will call the patient and/or dispensing pharmacy on Day 1 (+1 day) to confirm patient is in receipt of medication.

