3.1 Investigational Study Medications

Patients who present with uUTI symptoms, have a urine dipstick analysis positive for both leukocyte esterase AND nitrite who meet all of the inclusion and none of the exclusion criteria, and who agree to participate in the study, will be treated for their uUTI with ciprofloxacin.

The ciprofloxacin, or a pharmacy prescription for ciprofloxacin, will be provided to the patient by the enrolling study site. Patients will be asked to take one 250 mg tablet or capsule twice daily (day 1 to 3 + 1 day) for 3 days. In the event a patient's first dose is taken in the PM on Day 1, the patient will be expected to take an AM dose on Day 4 to complete the 6 doses of ciprofloxacin, and the EOT visit will occur on day 4 instead of day 3.

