5.3 Drug Storage and Drug Accountability

Drug should be stored by the patient according to the guidance provided by the site or pharmacy. For drug accountability, the site will provide the patient with a diary to collect daily ingestion of ciprofloxacin. The patient should return the diary to the clinic along with the prescription bottle/container after completion of their ciprofloxacin course of treatment. Site staff will keep diary in source and record in the CRF.

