- Sensitivity Analysis 2: Will follow the same definition of clinical response defined in section 5.3 except, frequency is excluded and considering all other symptoms are resolved and no new uUTI symptoms.
- Sensitivity Analysis 3: Will follow the same definition of clinical response defined in section 5.3 except, improvement of symptoms (instead of resolution) from baseline and no worse than mild from baseline and no new uUTI symptoms are considered.
- Sensitivity Analysis 4: Will follow the same definition of clinical response defined in section 5.3 except, improvement of symptoms (instead of resolution) from baseline and no new uUTI symptoms are considered.
- Sensitivity Analysis 5: Will follow the same definition of clinical response defined in section 5.3 except, urgency and frequency are improved and no worse than mild from baseline and all other symptoms are resolved and no new uUTI symptoms are considered.

• Investigator response:

Investigator-determined response will use the definitions below to document response at Day 3 or Day 4 (+ 1 day) (EOT) and Day 12 (+/- 1 day) (TOC) in the ITT, m-MITT, CE-EOT, CE-TOC, ME-EOT and ME-TOC populations.

Clinical response	Definition			
Clinical cure	All pre-therapy signs and symptoms of the index infection had resolved such that no additional antibiotics were required			
Clinical failure	Patients who met any one of the criteria below were considered as failure:			
	Death related to uUTI prior to Day 3 or Day 12, respectively			
	No apparent response to treatment; persistence or progression of most or all pre-therapy signs and symptoms or use of additional antibiotics for the current infection			
	Patient previously met criteria for failure			

Clinical response	Definition
Indeterminate	Study data were not available for evaluation of efficacy for any reason, including:
	Patient lost to follow-up or assessment not undertaken such that a determination of clinical response could not be made at either the EOT or TOC visit
	Death prior to Day 3 or Day 12, respectively, where uUTI was clearly noncontributory

- Patient Symptom Assessment Questionnaire (filled out by patient) at Day 3 or Day 4 (+ 1 day) (EOT) and Day 12 (+/- 1 day) (TOC) in the ITT, m-MITT, CE-EOT, CE-TOC, ME-EOT and ME-TOC populations
- Overall response at Day 3 or Day 4 (+ 1 day) (EOT) in the ITT, m-MITT, CE-EOT and ME-EOT populations

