7.5 Study Drug Exposure and Compliance

All patients should be informed that compliance with taking all oral medication as instructed is imperative. A site designee will phone the patient or the pharmacy on Day 1 to ensure that the prescription of ciprofloxacin was picked up and the first dose was taken. This phone call should be documented in the patient's source.

Patients will receive a dosing diary on Day 1 and be asked to record the dosing administration for the duration of the treatment period. The total amount of oral dosing completed during the treatment period will be documented in the eCRF.

A dosing summary will be presented for the ITT, m-MITT, CE and ME populations. The distribution of patients by the number of active doses of study drug therapy will be presented.

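### For women who start in the morning, the schedule allows an EOT visit on Day 3 before the sixth dose is due, with no later check of that dose and no SAP rule separating assessments made before and after the course ends

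*Protocol*

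**What the plan says.** Protocol 3.1 gives the regimen: "Patients will be asked to take one 250 mg tablet or capsule twice daily (day 1 to 3 + 1 day) for 3 days". For an evening start the same section says "the patient will be expected to take an AM dose on Day 4 to complete the 6 doses of ciprofloxacin", which fixes the course at six doses; Protocol 5.2.2 repeats this.

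The EOT visit follows the start time. Footnote 1 to the schedule says of a first dose "taken in the morning on Day 1, the EOT visit will be on day 3 (+1 day", and of one "taken in the evening on Day 1, the EOT visit will be on day 4 (+1 day". SAP Appendix 1 carries the same footnote.

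Protocol 6.2.2 lists what happens at EOT: urine culture, symptom questionnaire, investigator's assessment of response, compliance check and collection of the dosing diary. Protocol 5.3 sets a different point for the diary: "The patient should return the diary to the clinic along with the prescription bottle/container after completion of their ciprofloxacin course of treatment".

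On the analysis side, SAP 6.3 defines the EOT window by study day alone. SAP 5.3 reports microbiologic, clinical and investigator response at EOT, and also "Overall response at Day 3 or Day 4 (+ 1 day) (EOT) in the ITT, m-MITT, CE-EOT and ME-EOT populations". SAP 7.5 adds: "The distribution of patients by the number of active doses of study drug therapy will be presented".

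**The concern.** The label EOT implies that treatment has ended. For evening starters the protocol moves the visit to Day 4, the day of the sixth dose, so the drafters evidently meant the visit to track the dosing pattern. For morning starters, the nominal Day 3 visit does not ensure that the course is complete.

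Two things are at stake. First, EOT response may combine women assessed after five doses with women assessed after all six, and nothing in the SAP tells them apart. Second, the dose record may be cut short. If the diary is handed in on Day 3, the sixth dose has no scheduled point of capture, and a woman who took every dose can appear in the exposure table as having taken five.

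**Working it through.** **Inputs.** Two doses a day for 3 days (Protocol 3.1); six doses in all (Protocol 3.1 and 5.2.2); EOT on Day 3 (+1 day) for a morning start and Day 4 (+1 day) for an evening start (footnote 1); at least four doses for the clinically evaluable (CE) population (SAP 4.5).

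**The plan's own figure.** 2 × 3 = 6 doses, which agrees with the stated six.

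**Doses due by each permitted EOT day.**

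| Start | Dose slots | EOT day | Due before that day | Due once that day's morning dose is taken | Due by end of day |
|---|---|---|---|---|---|
| Morning | D1 AM, D1 PM, D2 AM, D2 PM, D3 AM, D3 PM | 3 | 4 | 5 | 6 |
| Morning | as above | 4 | 6 | 6 | 6 |
| Evening | D1 PM, D2 AM, D2 PM, D3 AM, D3 PM, D4 AM | 4 | 5 | 6 | 6 |
| Evening | as above | 5 | 6 | 6 | 6 |

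At a daytime Day 3 visit a fully compliant morning starter has therefore taken at most 5 of 6 doses (5/6 = 83%).

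**Clock check.** The documents give no clock times, so assume 12-hour spacing. Dose 6 comes 5 × 12 = 60 hours after dose 1. For a first dose at hour t on Day 1, it falls on Day 3 at t + 60 − 48 = t + 12. A first dose between 06:00 and 11:59 puts dose 6 between 18:00 and 23:59 on Day 3, so any Day 3 visit before 18:00 precedes it. A Day 4 visit at 08:00 comes 72 + 8 − (t + 60) = 20 − t hours after dose 6, that is, about 8 to 14 hours.

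**Can the sixth dose be recorded later?** The diary and the compliance check appear at EOT. Neither appears among the TOC activities (Protocol 6.3.1 and the schedule), and the Day 21 call asks only about symptoms (Protocol 6.3.2). No later contact is scheduled to confirm dose 6.

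**Does population membership change?** Four or five recorded doses both meet the CE minimum of four, so an otherwise compliant woman stays in the population.

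**How many women?** Let m be the share of women starting in the morning and f the share of those seen on Day 4. Ignoring late-evening Day 3 visits, the number assessed before the last dose is 250 × m × (1 − f). The documents give neither m nor f. As f runs from 1 to 0, the affected share of morning starters runs from 0% to 100%.

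**The case against.** The best case for the plan is that footnote 1 sets a window. A Day 4 visit is compliant, follows dose 6 and satisfies Protocol 5.3; a late Day 3 evening visit could too. The EOT visit also sits openly under the treatment period in Protocol 6.2 and the schedule, and the post-treatment assessment is Day 12. Protocol 5.2.3 asks the CRF for total dosing over the treatment period, so a careful site could still enter six. EOT outcomes are additional and descriptive, and SAP 7.6 plans no hypothesis test.

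Much of that stands. It shows that the conflict can be avoided, but the plan does not require sites to avoid it: Day 3 is the nominal day, and a site that follows it during clinic hours collects the diary early. The instruction to record total dosing does not say how the site learns of a dose taken after the last compliance check.

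A reader might go further in three ways that the documents do not support.

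- **That EOT mixes on-drug and off-drug urine, so eradication is overstated in morning starters.** An evening starter seen on Day 4 takes her sixth dose that morning, and a morning starter seen on Day 3 has also just had a morning dose. Both can be only hours past a dose; what differs is five doses against six. Neither document gives urinary drug levels or carry-over data from which suppressed growth could be argued.
- **That every morning starter is affected, or that a percentage of the 250 can be stated.** The Day 4 option rules out the first, and the unknown shares rule out the second.
- **That all EOT outcomes are reported in six populations.** Microbiologic, clinical and investigator response are; overall response at EOT is reported in four.

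**Conclusion.** The concern holds in a limited form. Followed as written, the schedule can place EOT before the last dose for morning starters, contrary to Protocol 5.3 on diary return. It can also leave the sixth dose uncaptured for the SAP 7.5 dose distribution. SAP 5.3 and 6.3 then pool assessments made before and after course completion.

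The effect per woman is one dose in six. The number of women is unknown. The conclusion assumes roughly 12-hour dosing and daytime clinic visits; neither is stated in the documents, but the dose count by day does not depend on exact times. The consequences are confined to the descriptive EOT summaries and the exposure table. The Day 12 primary outcome definition does not use EOT timing, and CE membership does not change for an otherwise compliant woman. A correction is worth making because the inconsistency is clear and inexpensive to resolve.

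**What to change.** - **Protocol 5.3, Protocol 6.2.2 and footnote 1 in both appendices:** reconcile these so that the EOT assessments and the collection of diary and container are consistent with completion of the course. Leave dosing unchanged.
- **CRF:** record the date and time of the last dose. Where a dose was still due at the EOT visit, confirm afterwards whether it was taken, so that the dose count is complete. Because visit and last dose can fall on the same day, the split below also needs the time of the EOT specimen, or a yes/no entry on whether the last dose had been taken.
- **SAP 5.3:** report EOT microbiologic, clinical and overall response by whether the assessment came before or after the last dose, with a separate row where this cannot be recovered. Describe the groups as before or after course completion, not as on-drug or off-drug urine.

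The cost is one CRF field (two if specimen time is not already held), one extra split of descriptive tables, and possibly some loss of scheduling flexibility for morning starters. The Day 12 analysis needs no change.
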